# Table 5-2D: Sequential Monitoring Plan of Day 30 Grade 4 or Higher Capillary LeakSyndrome in 47 Patients

Number of Evaluable Patients	Rejection Boundary for Number of Day 30 Events
1	
2-7	2
8-18	3
19-29	4
30-39	5
40-47	6

The actual operating characteristics of the truncated test are shown in Table 5-2E, obtained from a simulation study that assumed uniform accrual of 47 patients over a 365-day period with 395 days of monitoring.

# Table 5-2E: Operating Characteristics of the Binary SPRT for Day 30 Grade 4 or Higher Capillary Leak Syndrome from a Simulation Study with 100,000 Replicates

True Day 30 Grade 4 or Higher CLS Rate	5%	10%	15%	20%
Probability Reject Null	0.094	0.466	0.807	0.954
Mean Month Stopped	12.3	9.9	7.3	5.4
Mean # CLS events by Day 30	2.2	3.5	3.7	3.5
Mean # Patients Enrolled	44.7	36.8	27.8	21.1

The testing procedure rejects the null hypothesis in favor of the alternative 9.4% of the time when the true Day 30 Grade 4 or higher CLS rate is 5% and 80.7% of the time when the rate is 15%. This corresponds to a type I error rate of 9.7% and a type II error rate of 19.3%. If the true Day 30 Grade 4 or higher CLS rate is 15%, the DSMB will be consulted 220 days after opening on average, when 4 events have been observed in 28 patients.

# 5.2.3 Demographic and Baseline Characteristics

Demographic and baseline characteristics will be summarized for all patients. Characteristics to be examined are: age, gender, race/ethnicity, performance status, primary disease, primary disease status, disease risk index (DRI), time from steroid initiation to enrollment, acute GVHD grade and organ staging, graft source, GVHD prophylaxis, conditioning regimen, time from disease diagnosis to transplant, time from transplant to enrollment, and time from acute GVHD onset to enrollment.

Counts and percentages will be used to describe categorical variables, while the median, mean, standard deviation, and range will be used to summarize continuous variables.

# 5.3 ANALYSIS OF PRIMARY ENDPOINT

The primary endpoint of this trial is the proportion of patients that attain a Day 28 CR. Patients in a CR at Day 28 post-initiation of T-Guard treatment will be considered a success while all other patients will be considered a failure for this endpoint. The CR rate at Day 28 will be estimated in the primary analysis population (all patients that initiate T-Guard treatment) using the sample proportion and a 95% Wilson score or Clopper-Pearson CI, where appropriate.

The primary determination of efficacy of T-Guard treatment on Day 28 CR will be evaluated using efficacy and futility boundaries from the Simon's two-stage minimax design described in Section 5.2.1.

# 5.4 ANALYSIS OF SECONDARY ENDPOINTS

All secondary endpoints will be reported for the primary and PP analysis groups.

## **Key Secondary Endpoints**

## 5.4.1 Duration of Complete Response (DoCR)

DoCR is defined in Section 3.4. DoCR will be evaluated both in the set of all patients who achieve a CR and only in those patients who are in CR at Day 28 post-initiation of T-Guard

treatment. Estimates and 95% CIs for the median and quartiles of DoCR will be obtained using the Kaplan-Meier estimator.

# 5.4.2 Overall Survival (OS)

OS is defined as survival of death from any cause. The time from initiation of T-Guard treatment until death from any cause will be described using the Kaplan-Meier estimator. An estimate and 95% CI for OS at Days 90 and 180 post-initiation of T-Guard will be provided.

## Other Secondary Endpoints:

# 5.4.3 Overall Response Rate (ORR)

Overall response is defined as either a complete or patient response (CR+PR). The ORR will be estimated at Days 14, 28, and 56 post T-Guard initiation using sample proportions and 95% Wilson score or Clopper-Pearson CIs, as appropriate.

# 5.4.4 Proportion of Response

The proportion of patients in each aGVHD response category (CR, PR, MR, NR, or progression) will be described at Days 7, 14, 28, and 56 using sample proportions.

# 5.4.5 Non-relapse Mortality (NRM)

NRM is defined as death from any cause other than malignancy relapse/progression. The time from initiation of T-Guard until NRM will be described using the Aalen-Johansen estimator, with malignancy relapse/progression treated as a competing risk. Estimates and 95% CIs of the cumulative incidence of NRM will be provided at Days 100 and 180 post- initiation of T-Guard.

# 5.4.6 Relapse-free Survival (RFS)

RFS is defined as being alive and free of malignancy relapse/progression. The time from initiation of T-Guard until malignancy relapse/progression or death will be described using the Kaplan-Meier estimator. An estimate and 95% CI for RFS at Day 180 post-initiation of T- Guard will be provided.

# 5.4.7 GVHD-free Survival

GVHD-free survival is defined as being alive, in CR, and free of cGVHD. The proportion of patients with GVHD-free survival at Days 90 and 180 post-initiation of T-Guard will be estimated using the sample proportion and 95% Wilson score or Clopper-Pearson CIs, as appropriate, if no censoring occurs prior to Day 180. If censoring does occur, Days 90 and 180 GVHD-free survival will be assessed using the Aalen-Johansen estimator in an illness- death multi-state model.

# 5.4.8 Chronic GVHD (cGVHD)

cGVHD severity is defined per the 2014 NIH Consensus Criteria (see Appendix D). The time from initiation of T-Guard treatment until onset of cGVHD of any severity (mild, moderate, or severe) will be described using the Aalen-Johansen estimator, with death prior to cGVHD onset treated as a competing risk. An estimate and 95% CI of the cumulative incidence of cGVHD will be provided at Day 180 post-initiation of T-Guard. The maximum severity of cGVHD through Day 180 post-initiation of T-Guard will be tabulated.

# 5.4.9 Relapse/progression of the Underlying Malignancy

The time from initiation of T-Guard until malignancy relapse/progression will be described using the Aalen-Johansen estimator, with death prior to relapse/progression treated as a competing risk. An estimate and 95% CI of the cumulative incidence of malignancy relapse/progression will be provided at Day 180 post-initiation of T-Guard.

### 5.4.10 Incidence of Systemic Infections

The frequency of Grade 2-3 infections occurring from the initiation of T-Guard treatment until 28 days post-last dose will be tabulated by disease site, date of onset, and severity, with Grade defined per the BMT CTN Technical MOP. The cumulative incidence of Grade 2-3 infections at 28 days post-last dose will be described using the Aalen-Johansen estimator and its 95% CI, with death prior to infection treated as a competing risk.

#### 5.4.11 Incidence of Toxicities

The frequency of Grade 3-5 toxicities per CTCAE version 5 occurring from the initiation of T-Guard treatment until 28 days post-last dose will be tabulated by organ system. The maximum severity of reported toxicities during that period will also be summarized.

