# 1.3.2.3 Single-arm, Phase 1/2 Clinical trial in second line SR-aGVHD Patients

Following the promising results of T-Guard for the indication SR-aGVHD in the investigatorinitiated dose escalation study, a Phase 1/2 study XEN/TG-001 was conducted (Groth, van Groningen et al. 2018). The study was designed to evaluate the safety and efficacy of T- Guard in treating SR-aGVHD patients who were refractory to first-line therapy. Regarding the IMP (T-Guard), a switch was made to non-glycosylated bacterial produced recombinant RTA. In total 20 patients were treated with T-Guard with a dose of 4 mg/m^2 every other day x 4 doses. All patients had SR grade II to IV aGVHD. Seventeen of these patients (85%) had severe SR-aGVHD, and all 20 patients had visceral involvement; 18 GI (90%) and 5 liver (25%) involvement. Sixteen patients (80%) had 2 or more organs involved. A validated two biomarker algorithm classified the majority of patients (11/20) as high-risk.

The Day 28 ORR (primary endpoint), defined as having a CR or PR without the need for initiation of other treatments due to insufficient response, was 60%. Day 28 CR was 50% and PR 10%. The Day 180 OS was 60%. The outcomes achieved were very favorable compared with the historical standard of care (SoC) data at the participating centers (Day 28 CR less than 20% and Day 180 OS 29%).

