#### Preferred Term (≥5 Patients in Total) for TEAEs, Overall Study

System organ class/ Preferred term	Total (N=20) n (%)
Hypoalbuminemia	8 (40.0%)
Hyperglycemia	7 (35.0%)
Hypokalemia	5 (25.0%)
Hypophosphatasemia	5 (25.0%)
General disorders and administration site conditions	16 (80.0%)
Edema peripheral	8 (40.0%)
Pyrexia	8 (40.0%)
Fatigue	6 (30.0%)
Gastrointestinal disorders	15 (75.0%)
Nausea	5 (25.0%)
Investigations	13 (65.0%)
Blood bilirubin increased	6 (30.0%)
White blood cell count decreased	5 (25.0%)
Musculoskeletal and connective tissue disorders	13 (65.0%)
Muscular weakness	5 (25.0%)
Myopathy	5 (25.0%)
Vascular disorders	12 (60.0%)
Capillary leak syndrome	8 (40.0%)
Blood and lymphatic system disorders	11 (55.0%)
Anemia	6 (30.0%)
Thrombocytopenia	6 (30.0%)
Nervous system disorders	11 (55.0%)

In total 29 Serious Adverse Events (SAE) were reported in 14 patients (Table 1-2). Of those SAEs, 23 were reported as severe, 4 as moderate and 2 as mild. Eight (8) patients died during the course of the trial. The causes of death were determined to be refractory aGVHD, infections or the combination of the two. All deaths were reported as not related to T-Guard. No deaths occurred before 6 months (Day 180) due to relapse of the underlying disease.

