# 1.3.3 Justification for the Proposed Dose Regimen for this Phase III Clinical Trial Using T-Guard as First Line SR-GvHD Treatment

The proposed dose for the T-Guard Phase 3 study is  $4 \text{ mg/m}^2$  / dose q 48 hours x 4 doses. This dose is based on the following data:

In the investigator-initiated dose-escalation study (van Oosterhout, van Emst et al. 2000, van Oosterhout, van Emst et al. 2001) it was determined that the second dose level of 4 mg/m^2/dose q 48 hours x 4 doses delivered positive biological and clinical responses, without inducing any severe acute toxicities.

PK analysis showed that the 4 mg/m^2 x 4 doses schedule led to T-Guard *in vivo* serum  $C_{max}$  of around 1.5 µg/ml (~10^-8M). On basis of *in vitro* experiments, the  $C_{max}$  attained results in a 60-80% occupation of the target antigens CD3 and CD7. It has been shown in *in vitro* studies that this concentration is very effective in specifically eliminating antigen-positive target cells by RTA-based immunotoxins (Derocq, Laurent et al. 1987, Preijers, De Witte et al. 1988, Preijers, Tax et al. 1988, Herrera, Farah et al. 2000).

Given the 50% Day 28 CR rate observed in the T-Guard Phase 1/2 study, it could be argued that the clinical benefit may be further optimized by administering a higher T-Guard dose. When judging the response rate, though, consideration is given to the high incidence of serious comorbidities in this severely ill population. Four of the 20 patients of the T-Guard Phase 1/2 study died before Day 28 due to comorbidities; two patients died from sepsis (non- treatment related), one patient died in the treatment week with uncontrolled viral infections, and another patient had vanishing bile duct syndrome with very rare aberrant bile ducts at treatment start suggestive for co-existing liver disease of different etiology. When these four patients are censored, the Day 28 response rate increases to 63% CR (10/16) and 75% ORR (12/16), respectively. In the Phase 1/2 study, the adverse events judged to be potentially treatment-related were clinically manageable and included 7 mild cases (35%) and 1 moderate case (5%) of CLS.

To put the currently applied T-Guard dose in perspective, the Maximum Tolerated Dose as

[figure not shown]

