# 3.4.2.9 Incidence of Toxicities

All grade 3-5 toxicities according to CTCAE v5 occurring from the initiation of T-Guard treatment to 28 days post last dose will be described.

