# 4.4.4 Required Adverse Event Reporting

Any unanticipated SAEs from time of enrollment through the study defined follow up are required to be reported following the BMT CTN Administrative MOP Chapter 6. Additionally, any grade 4 anticipated event not collected on the calendar-driven toxicity or specified event- driven form must **also** be reported through the expedited AE reporting system in Advantage eClinical. Chapter 6 of the BMT CTN MOP defines reporting based on the terms Unexpected and Expected; however, for this study, the reporting will be based on the terms Unanticipated and Anticipated All adverse events, including SAEs, must be reported from the 1st dose of T- Guard through 30 days after the last dose. In addition, any SAEs occurring after that 30-day period, but assessed as related to the investigational product, must be reported. All SAEs are to be followed up until resolved, judged to be no longer clinically significant, or until they become chronic to the extent that they can be fully characterized.

Infections are collected separately in eClinical as this is a study endpoint; however, should an infection meet the SAE criteria the infection must also be reported following the SAE reporting criteria outlined above.

GVHD and underlying disease relapse events are also collected separately in eClinical because they are part of the endpoint analysis. Events of GVHD and underlying disease relapse are not to be reported as AEs/SAEs for this study.

The Sponsor has a list of events classified as Special Situations. These events are 1) medication error, 2) overdose and 3) pregnancy. These events must be reported following the reporting for SAEs.

SAEs that require reporting will be reported through an expedited AE reporting system via an EDC. All SAEs, as well as Special Situations, must be reported within 24 hours of knowledge of the event. Events entered in EDC will be reported using NCI's CTCAE Version 5.0. If there are network outages, a paper copy of the AE form must be completed and emailed to Emmes to initiate Sponsor review. Once the system is available, the event information must be entered into the system.

Anticipated AEs will be reported using NCI's CTCAE Version 5.0 at regular intervals as defined on the Form Submission Schedule, including calendar-driven eCRFs (e.g., Toxicity and GVHD) or event-driven eCRFs (e.g., Relapse/Progression, Infection, Secondary Graft Failure and Death).

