# Table 5-2C: Operating Characteristics of the Binary SPRT for Day 30 Overall Mortalityfrom a Simulation Study with 100,000 Replicates

The testing procedure rejects the null hypothesis in favor of the alternative 9.6% of the time when the true Day 30 mortality rate is 15% and 81.4% of the time when the rate is 30%. This corresponds to a type I error rate of 9.6% and a type II error rate of 18.6%. If the true Day 30 mortality rate is 30%, the DSMB will be consulted 220 days after opening on average, when 7 events have been observed in 28 patients.

CTCAE Grade 4 or higher capillary leak syndrome (CLS) is another key safety endpoint that will be monitored during this study. The rate of Grade 4 or higher CLS occurring within 30 days following T-Guard initiation will be monitored in patients who initiate this treatment. This monitoring will compare a null rate of 5% to an alternative rate of 15%, considered to be unacceptable, using a sequential probability ratio test (SPRT) for binary data. The SPRT can be displayed in a tabular form, as shown in Table 5-2D. This table gives the rejection boundaries for the number of Day 30 CLS events corresponding to the number of evaluable patients. At least two events must be observed in order to trigger review. Figure 5-2B displays the same information in a graphical format.

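### No planned analysis estimates the incidence of Grade 1-2 capillary leak syndrome, although CLS is a key safety endpoint and every Phase I/II case was rated mild or moderate

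*Combined protocol and SAP*

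**What the plan says.** The toxicity endpoint in Section 3.4.2.9 covers "All grade 3-5 toxicities according to CTCAE v5" from the start of treatment to 28 days after the last dose. Section 5.4.11 carries this into the analysis, grouped by organ system: "The frequency of Grade 3-5 toxicities per CTCAE version 5 occurring from the initiation of T-Guard treatment until 28 days post-last dose will be tabulated". A further sentence there adds a summary of maximum severity.

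CLS also has its own monitoring rule. Section 5.2.2 (text after Table 5-2C) says "CTCAE Grade 4 or higher capillary leak syndrome (CLS) is another key safety endpoint" and sets up a sequential test of a 5% against a 15% rate within 30 days of the first dose. Section 5.5.6 summarises related SAEs by type.

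Collection is wider than analysis. Section 4.4.4 states: "All adverse events, including SAEs, must be reported from the 1st dose", up to 30 days after the last one, with no grade floor.

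On earlier experience, Table 1-1 gives CLS in 8 of 20 Phase I/II patients. The dose justification in Section 1.3.3 says the potentially related events "included 7 mild cases (35%) and 1 moderate case (5%) of CLS". The note to Table 1-2 says CTCAE 4.0 was used for every event except CLS, which was graded on a separate published system.

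**The concern.** The protocol treats CLS as important. Section 1.3.3 describes it as the toxicity that most often limits the dose of comparable ricin-A-chain immunotoxins. Section 2.5.5 gives it its own guidance for withholding treatment, and Section 5.2.2 makes it a key safety endpoint. The case for the chosen dose also draws on the all-grade CLS profile from Phase I/II.

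The analysis chapter would nevertheless not update that profile. The toxicity table starts at Grade 3 and the monitoring rule at Grade 4, while the only CLS seen in Phase I/II was rated mild or moderate. The trial is meant to confirm the safety of this regimen, and it could end with no planned estimate of how often CLS occurs, although adverse events of all grades will have been reported.

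**Working it through.** **1. The plan's own figure.** Section 1.3.3 gives 7 mild and 1 moderate case in 20 patients. 7/20 + 1/20 = 8/20 = 40%, which agrees with Table 1-1. Table 1-2 shows one CLS case in its Grade 2 column, which matches the one moderate case. No case was rated severe: 0/20.

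**2. Which planned analysis would report CLS, by grade**

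| CTCAE grade | 5.4.11 toxicity table | 5.2.2 monitoring | 5.5.6 related SAEs |
|---|---|---|---|
| 1-2 | No | No | Only if a related SAE |
| 3 | Counted by organ system; display by term not required | No | Only if a related SAE |
| 4-5 | Counted by organ system; display by term not required | Yes, as a DSMB trigger | Only if a related SAE |

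Chapter 5 plans no all-grade adverse event table and no final CLS proportion with an interval.

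**3. Precision of the Phase I/II rates.** Exact (Clopper-Pearson) 95% limits are the 2.5% quantile of Beta(x, n − x + 1) and the 97.5% quantile of Beta(x + 1, n − x).
- Any grade, x = 8, n = 20: 19.1% to 63.9%.
- Severe, x = 0, n = 20: upper limit 1 − 0.025^(1/20) = 16.8%.

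**4. Carried to the 47 treated patients planned in Section 5.1**
- Any grade: 47 × 0.40 = 18.8, about 19 (9.0 to 30.1 over the interval).
- Grade 3 or higher, taking mild and moderate as below Grade 3: 47 × 0 = 0 at the point estimate, and 47 × 0.168 = 7.9 at the upper limit.
- Grade 4 or higher at the plan's null rate of 5%: 47 × 0.05 = 2.35.

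**5. What an all-grade row would deliver.** If 19 of 47 patients had CLS, the estimate would be 40.4% with an exact 95% CI of 26.4% to 55.7%.

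**6. Whether the data exist in the right window.** With dosing on Days 0, 2, 4 and 6, the 5.4.11 window closes on Day 6 + 28 = Day 34. If dosing runs to Day 14, it closes on Day 42. Calendar toxicity recording in Section 4.3.2 starts on Day 56, after both. The adverse event reports under Section 4.4.4 run to 30 days after the last dose, so they cover the window and are the natural source.

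**The case against.** Several points on the other side have force.

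- **Scale.** Phase I/II CLS was not graded on CTCAE, so mild and moderate cannot be equated with certainty to CTCAE v5 below Grade 3. A reader might infer that the final report will show almost no CLS. The documents do not support that: the mapping is unknown, and 0/20 still allows about 8 of 47 patients at Grade 3 or higher. This point stands, and the size is therefore stated conditionally.
- **Importance and cause.** A reader might call CLS the drug's main known harm, caused in 40% of patients. Section 1.3.2.4 names hypoalbuminemia and thrombocytopenia as the most commonly reported related events. The statement on dose limits concerns similar agents. The 8 cases are treatment-emergent, potentially related events from an uncontrolled study. The stronger reading falls.
- **Layout.** Tabulation by organ system does not say that individual terms are suppressed. Table 1-1 uses organ class with terms beneath it and lists CLS by name, so Grade 3 CLS may well be visible. It is only not required to be.
- **Maximum severity.** The second sentence of Section 5.4.11 states no grade floor of its own. But it follows a Grade 3-5 restriction that matches the endpoint in Section 3.4.2.9, and on any reading it does not call for results by term. It gives no CLS incidence.
- **Oversight.** The DSMB sees toxicities and adverse events at least twice a year, with full reviews after 10 and 30 evaluable patients, and CLS is monitored monthly. This protects patients during the trial. It is not a final estimate.
- **Interpretation.** Edema, nausea and low albumin overlap with the underlying illness, so low-grade CLS is hard to read in a single-arm, open-label trial. That limits what the row can show. It does not justify having no row for a key safety endpoint.
- **Grading.** Section 4.4.2 requires a severity grade for unanticipated SAEs. Section 4.4.4 applies CTCAE v5 to events entered in the data system. Grading of non-serious CLS is likely but not spelled out.

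**Conclusion.** The point holds as a gap in planned tabulation, not in data capture or in safety monitoring. As written, no analysis estimates Grade 1-2 CLS, and Grade 3 CLS need not be shown by name unless it is a related SAE. If the earlier ratings correspond to below CTCAE Grade 3 and the 40% rate carries over, about 19 of 47 patients could have CLS with few or none of them in the Grade 3-5 table. Both conditions are assumptions: the first cannot be checked because the earlier scale is not reproduced in the documents, and the second rests on 20 patients. The change is a cheap improvement worth making, because it decides whether the trial can state a CLS incidence at all.

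**What to change.** Add to Sections 3.4.2.9 and 5.4.11: the number and proportion of treated patients with CLS of any grade, by maximum CTCAE v5 grade, shown as its own row. Use the 95% Wilson or Clopper-Pearson interval already used for proportions. Keep the existing 5.4.11 window, from first dose to 28 days after the last dose, and name the adverse event data required by Section 4.4.4 as the source. Confirm that non-serious CLS entries carry a CTCAE v5 grade.

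State that comparison with Phase I/II is limited to any-grade incidence, because the grading scales differ, and note the overlap of low-grade CLS with signs of the underlying illness.

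The cost is one extra table and a sentence in each section. The adverse events are already to be reported, and dosing, withholding and stopping rules are untouched.

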#### 5.4.12 Pharmacokinetics

A population pharmacokinetic model will be developed for T-Guard based on the SPV-T3a- RTA and WT1-RTA levels measured in samples obtained before each infusion and at pre- defined timepoints after infusion (Table 4.2). The model will be used to evaluate the following metrics:

- Cinf: Observed and model-predicted concentration at the end of infusion
- CL: Systemic clearance
- AUC: Model-predicted area under the curve from the start of the current infusion until the next infusion or until 48 hours following for the last infusion
- t1/2: Model-predicted terminal half-life
- Vc: Volume of the central compartment

Additionally, the impact of various factors on these measures will be evaluated, including age, weight, BSA, BMI, disease status, and ADA.

